## **2. Subsequent Visits**

### Study Visit

Participants who are medically approved to take part in the study after the screening visit are invited to take part in the study visit. Prior to the study visit, and after the screening visit, participants will be randomised using the variance minimisation algorithm described above to ensure a balance of covariates of interest across treatment and placebo groups. The randomisation code will be drawn up by a researcher not involved in the study using an randomisation procedure known as variance minimisation, following a procedure outlined by Sella, Raz & Cohen Kadosh (2021). Participants will be allocated to placebo or treatment groups based on gender, level of education, and their digit span score (as an index of general intelligence). Allocation of treatments will be recorded on a Randomisation List which will be updated when each new participant enters the randomised phase. The Randomisation List will be held securely within the Neurosciences Building by the study medic ([name]). Pitolisant and placebo agents will be kept securely within a locked medicines cabinet also within the Neurosciences building.

During the visit, participants will receive either a single dose of pitolisant (36mg single dose) or placebo. They will receive the dose at the Neurosciences Building, Warneford Hospital site. The study has a double-blind design thus neither the researchers nor the participant will know whether pitolisant or placebo is given. On arrival, participants will briefly be reviewed to ensure the inclusion criteria are still satisfied. Prior to drug or placebo administration, the following procedures will be undertaken:

- Inclusion/exclusion criteria review

- Completion of the MRI screening form (APPENDIX H - 3T VOLUNTEER SCREENING FORM) once more to ensure it is still safe for them to undergo fMRI scanning.
- Clinical screening, mood and side effects questionnaires (to establish baseline) on qualtrics – PHQ-9, GAD-7, PANAS, PDQ and Need for Cognition Scale

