### 5. Discontinuation/Withdrawal of Participants

Each participant has the right to withdraw from the research at any time. In addition, the Investigator may discontinue a participant from the research at any time if the Investigator considers it necessary for any reason including:

- Pregnancy
- Ineligibility (either arising during the research or retrospectively having been overlooked at screening)

- Significant protocol deviation
- Significant non-compliance with treatment regimen or research requirements
- Withdrawal of consent
- Loss to follow up

If a participant is withdrawn, no further procedures or observations will continue to be required. Withdrawal from the study will result in exclusion of the data for that participant from analysis. Withdrawn participants will be replaced. The reason for withdrawal if given will be recorded in the Participant Log of the Research Master File.

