**2. Provide details about the safety monitoring of participants and the staff/researchers carrying this out**

On the study visit, where the participant will either take a single dose of pitolisant or placebo, participants will be advised to have not consumed alcohol within the past 24 hours. Participants will be asked to arrive via walking or public transport or taxi, and will be asked to continue to avoid driving, operating heavy machinery or using a bicycle for at least the following 12 hours (maximum half-life of pitolisant). All participants will receive a phone number for calling an out-of-hours BRC on-call medic service in case they need medical advice related to the study after the study visit has taken place.

The randomisation code will be broken if a participant requires treatment for a new medical condition/experiences serious adverse reactions and either of these situations make it clinically important to know what medication they are taking. In order to unblind the participant, the study medic/delegated medic will have access to the randomisation code and can unblind if necessary within a maximum of 1 hour. If breaking the code is necessary then only that individual's code will be broken. Data from unblinded participants will not be admitted to analysis. If unblinding occurs, the researcher will record the reason and result of the unblinding, as well as the date and time of the event.

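### Sections G.5 and I.3.2 discard scan and task data already collected under blind when a dosed participant is later withdrawn or unblinded, so exclusions can differ by arm

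*Protocol*

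**What the plan says.** Section G.5 lets a participant leave at any time and also gives the study team wide discretion: "the Investigator may discontinue a participant from the research at any time if the Investigator considers it necessary for any reason". The listed reasons include "Ineligibility (either arising during the research or retrospectively having been overlooked at screening") and "Loss to follow up". The consequence is the same for every reason: "Withdrawal from the study will result in exclusion of the data for that participant from analysis. Withdrawn participants will be replaced".

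Section I.3.2 provides for breaking the code when a participant needs treatment for a new medical condition or has serious adverse reactions, and "either of these situations make it clinically important to know what medication they are taking". It then says: "Data from unblinded participants will not be admitted to analysis". It does not say whether unblinded participants are replaced.

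The timing comes from Section G.2: "Prior to the study visit, and after the screening visit, participants will be randomised". Dosing, a two-hour wait, the scan and the remaining tasks all fall on one day. A mood and side-effects questionnaire follows the next day. Section I.3.2 also gives participants an on-call medical number "in case they need medical advice related to the study after the study visit has taken place".

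Nothing in the protocol keeps data recorded before withdrawal or unblinding, and no sensitivity analysis is described.

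**The concern.** Randomisation protects the comparison only if people stay in it for reasons that treatment does not influence. Both rules remove people after randomisation, and some of the triggers are post-dose events that the drug could cause. The section on adverse reactions cites side effects (increased sleep duration, dystonia, dizziness) in 1 in 6 healthy volunteers after a single 40 mg dose, so a link with tolerability is possible. If those who feel unwell on pitolisant also perform worse, removing them makes the pitolisant arm look better than it is.

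The rule is also unnecessary for data recorded before the event. A code broken after the visit cannot alter a scan or task result obtained under blind. Because the protocol itself fixes both exclusions, a SAP that kept these data would contradict it.

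**Working it through.** **1. When can the rules remove usable data?**

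| Event | Scan and task data exist? | Effect of the rule |
|---|---|---|
| Leaves before the scan | No | Nothing to discard; no rewording recovers it |
| Stops part-way through the post-scan tasks | Scan and some tasks | Scan and completed tasks discarded |
| Code broken after the visit (I.3.2) | Complete | All discarded, automatically |
| Treated as lost to follow-up after the next-day questionnaire is missed (G.5) | Complete | All discarded if the investigator discontinues |
| Ineligibility found retrospectively (G.5) | Possibly complete | All discarded if the investigator discontinues |

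**2. The plan's own sizing (Section J.3).** Inputs: one-way ANOVA, effect size 0.4, alpha 0.05, power 80%, N = 52, plus 4 extra participants. With two groups, f = 0.4 corresponds to a difference of 2 × 0.4 = 0.8 SD. The noncentrality is f² × N.

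- N = 52: 0.16 × 52 = 8.32, df (1, 50), power 80.7%. The stated figure reproduces.
- N = 56: 0.16 × 56 = 8.96, df (1, 54), power 83.6%.

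The sample size is not in error; 0.8 SD serves below as a yardstick.

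**3. Bias by formula.** The protocol gives neither a withdrawal nor an unblinding rate, so these are assumptions: no true effect, losses in the pitolisant arm only, and a normally distributed liability to be lost that correlates ρ = 0.3 to 0.5 with a worse outcome. If a proportion q with the highest liability is removed and replaced, then

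bias (in SD) = ρ × φ(c) / (1 − q),

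where c is the upper-q point of the standard normal and φ its density.

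| Lost of 28 | q | c | φ(c) | Bias, ρ = 0.3 | Bias, ρ = 0.5 |
|---|---|---|---|---|---|
| 1 | 0.0357 | 1.803 | 0.0786 | 0.024 | 0.041 |
| 2 | 0.0714 | 1.465 | 0.1364 | 0.044 | 0.073 |
| 4 | 0.1429 | 1.068 | 0.2256 | 0.079 | 0.132 |

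**4. Bias and type I error by simulation.** 400,000 trials per cell, 28 per arm, two-sided t-test at 0.05. The k participants with the highest liability are lost, and m of them have usable outcomes. The rule drops all k; rewording keeps the m. Each pair is ρ = 0.3 / 0.5.

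| Loss pattern | Bias, lost participants replaced | Type I error | Bias, not replaced | Type I error |
|---|---|---|---|---|
| k = m = 1, one arm | 0.021 / 0.036 | 5.14 / 5.33% | 0.022 / 0.037 | 5.17 / 5.39% |
| k = m = 2, one arm | 0.039 / 0.065 | 5.30 / 5.98% | 0.041 / 0.069 | 5.31 / 5.97% |
| k = m = 4, one arm | 0.068 / 0.114 | 5.80 / 7.49% | 0.076 / 0.126 | 5.91 / 7.69% |
| 4 usable, split 3:1 | 0.032 / 0.054 | 5.37 / 5.91% | 0.037 / 0.062 | 5.32 / 6.11% |
| 4 usable, split 2:2 | 0.000 / 0.000 | 5.18 / 5.45% | 0.000 / −0.001 | 5.18 / 5.53% |

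Against the yardstick, one or two losses amount to 0.021/0.8 = 3% up to 0.069/0.8 = 9% of the effect used for sizing.

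**5. What rewording recovers.** With k = m = 1 or 2 and replacement, keeping the records returns the bias to 0.000. When some of the lost have no outcomes, only part is removable:

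- k = 2, m = 1, replaced: 0.039 / 0.066 in total, of which 0.020 / 0.034 is removable.
- k = 4, m = 2, replaced: 0.068 / 0.113 in total, of which 0.036 / 0.060 is removable.
- k = 4, m = 2, not replaced: 0.075 / 0.127 in total, of which 0.041 / 0.068 is removable.

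**The case against.** **The window is narrow.** This stands. There is one dose, and all scan and task outcomes come from the same day. A missed questionnaire is nowhere defined as withdrawal; discontinuation for it is discretionary. Reimbursement is processed at that contact and payment is made on completion, so participants have a reason to attend. A code break requires a medical event and a clinical need to know the allocation, and it affects usable data only if some outcomes have already been recorded.

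**The tolerability evidence is weak.** Largely right. The 1 in 6 is a side-effect frequency at 40 mg, not a withdrawal or unblinding rate, and the study dose is 36 mg. Sections E and I.3.4 expect little from a single dose. The figure shows that a link is possible, not how often it would operate, and it is not used above as a loss rate.

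**The type I figures are partly a modelling artefact.** This stands for the smallest cells. Trimming a fixed number of extreme values raises the error even in the 2:2 split, where there is no bias. Under a fixed-threshold exclusion model, one loss in one arm gives 5.0 to 5.2%, essentially nominal. For two losses the models agree (5.3 to 5.9%). The bias itself remains under the stated assumptions.

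**Excluding ineligible participants or major deviators is common in a mechanistic study, and some listed reasons have no obvious link to treatment.** Fair. The firm objection is to losing blinded records because of a later unblinding or a missed questionnaire. Withdrawal of consent to use the data is a separate and legitimate ground for exclusion.

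None of this shows that the rules spare data already collected. They do not.

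**Conclusion.** The concern holds, and the rules should be changed. As written, Sections G.5 and I.3.2 remove data recorded under blind for events after randomisation that treatment can influence, and replacement does not repair this.

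The expected effect is small. One or two usable losses confined to one arm give 0.02 to 0.07 SD and a type I error of about 5 to 6%. Four give 0.07 to 0.13 SD and 5.8 to 7.7%, an unlikely upper bound because the allowance of 4 also covers data quality and early leavers have no outcomes. Losses that are balanced across arms, or unrelated to outcome, cause no bias but still waste data in a 56-person trial. These sizes rest on an assumed loss pattern and correlation that the protocol does not supply; the text of the rules is not in doubt. The reason to act is that rewording is cheap now, and a change made after such events occur would lack credibility.

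**What to change.** Reword Sections G.5 and I.3.2 so that:

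- (a) randomised, dosed participants are analysed in their allocated arm with all outcome data collected before withdrawal or unblinding, unless they withdraw consent to the use of those data;
- (b) a missed next-day questionnaire does not remove scan and task data;
- (c) unblinded participants stay in the main analysis, with their exclusion as a sensitivity analysis;
- (d) any exclusion for ineligibility that existed before dosing is decided blind to allocation and outcome;
- (e) replacements add to, and do not substitute for, dosed participants with outcome data; those who leave before dosing may be replaced.

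Exclusions should be reported by arm with reasons.

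The cost is rewording two sections and running one sensitivity analysis. The amendment needs ethics approval (Section M). The information sheet and consent form, which are not shown, must be checked: if they promise removal of data on withdrawal, item (a) cannot be applied to people already consented on those terms. The downside is that a few incomplete or unblinded records enter the analysis. The change cannot recover outcomes for anyone who leaves after dosing but before the scan and tasks.

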#### 6. Definition of End of Study

The end of the study for participant involvement is the date of the last visit of the final participant.

#### 7. Please detail all expenses or gifts that will be offered to participants.

Guidance is available in [Best Practice Guidance: 05 Payments and incentives in research](#).

Participants will be paid £140 upon completion of their participation in the research. In addition, they may win up to £20 depending on the choices they make in some tasks. If they do not complete the study, they will be given a pro-rata amount to recompense the time they did spend in the study.

Reasonable travel expenses (up to £20 per visit) for any visits will be reimbursed on production of receipts, or a mileage allowance provided as appropriate.

## Section H. Interventions

### Drug/Substance 1

Name of drug/substance to be used	Pitolisant (Wakix)
Formulation, dose and route of administration for research	Two film-coated tablets (18mg x 2 [36mg]) for oral administration will be encapsulated in opaque capsules
Duration of treatment for research	Single dose
Licence status of this drug/substance	Active license from EMA and FDA for the treatment of narcolepsy with or without cataplexy in adults
Usual Indication	Adults with Narcolepsy with or without cataplexy
Usual Dose	4.5mg – 36mg per day
Usual duration of treatment	Continuous use
Where will drug/substance be sourced from?	Pharmacological Wholesaler via Oxford Health NHS FT
Where will drug/substance be stored at site?	Pitolisant will be stored within the Neurosciences Building at the Department of Psychiatry. It will be stored at room temperature in a locked cupboard, which is suitable for drug storage.
How will drug/substance be dispensed?	Pitolisant will be dispensed from the Neurosciences Building by a study medic or nurse.

How will the drug/substance be prepared by the researchers for use in this research?	Pitolisant will be encapsulated by trained clinical trial support staff using our Standard Operating Procedure.
---	---

Drug/Substance 2	
Name of drug/substance to be used	Lactose placebo
Formulation, dose and route of administration for research	Two placebo tablets will be encapsulated in opaque capsules.
Duration of treatment for research	One capsule; single dose
Licence status of this drug/substance	Single dose
Usual Indication	N/A
Usual Dose	N/A
Usual duration of treatment	N/A
Where will drug/substance be sourced from?	Placebo tablets will be sourced from HSC (www.hsconline.co.uk).
Where will drug/substance be stored at site?	Placebo tablets will be stored within the Neurosciences Building at the Department of Psychiatry. They will be stored at room temperature in a locked cupboard, which is suitable for drug storage.
How will drug/substance be dispensed?	Placebo tablets will be dispensed from the Neurosciences Building by a study medic or nurse.
How will the drug/substance be prepared by the researchers for use in this research?	Placebo tablets will be encapsulated by trained clinical trial support staff using our Standard Operating Procedure.

Section I. Safety	
1. Definitions	
Adverse Event (AE)	Any untoward medical occurrence in a participant to whom a substance has been administered, including occurrences which are not necessarily caused by or related to that substance.
Adverse Reaction (AR)	An untoward and unintended response in a participant to a substance, which is related to any dose administered to that participant. A causal relationship between the administered substance and an AE is at least a reasonable possibility, i.e. the relationship cannot be ruled out.
Serious Adverse Event (SAE)	A serious adverse event is any untoward medical occurrence that:

	
 
• results in death
 
• is life-threatening
 
• requires inpatient hospitalisation or prolongation of existing hospitalisation
 
• results in persistent or significant disability/incapacity
 
• consists of a congenital anomaly or birth defect.
 
 
Other 'important medical events' may also be considered serious if they jeopardise the participant or require an intervention to prevent one of the above consequences.
 
NOTE: The term "life-threatening" in the definition of "serious" refers to an event in which the participant was at risk of death at the time of the event; it does not refer to an event which hypothetically might have caused death if it were more severe.

Serious Adverse Reaction (SAR)	An adverse event that is both serious and, in the opinion of the reporting Investigator, believed with reasonable probability to be due to one of the research treatments, based on the information provided.
Suspected Unexpected Serious Adverse Reaction (SUSAR)	A serious adverse reaction, the nature and severity of which is not consistent with the information about the medicinal product set out in its summary of product characteristics (SmPC).

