## 2. Reporting procedures for serious adverse events or reactions

Any adverse event (AE) occurring to a participant will be reported to the MS IDREC. Reports of related (resulted from administration of any of the research procedures) and unexpected (the type of event is not listed in the protocol as an expected occurrence) adverse events will be reported as soon as possible once the Principal Investigator becomes aware of the event. Unrelated/expected adverse events will be reported within 10 working days of the Principal Investigator becoming aware of the event.

All SUSARs will be reported to the MHRA in addition to the MS IDREC. For fatal and life-threatening SUSARs, this will be reported as soon as possible, but no later than 7 calendar days after the PI is first aware of the reaction. Any additional relevant information will be reported within 8 calendar days of the initial report. Non-fatal or non-life-threatening SUSARs will also be reported as soon as possible, and no later than 15 days after the PI is first aware of the reaction.

All reports to the MHRA will be via the [Yellow Card Scheme](#).

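### The Serious Adverse Reaction definition asks for a stronger causal judgement than the Adverse Reaction definition, so an unexpected serious event with only a possible link to treatment can miss the MHRA report

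*Protocol*

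**What the plan says.** Section I.1 of the Protocol defines the safety terms in one table. Three rows matter here.

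- **Adverse Reaction (AR).** The causality test is low: "A causal relationship between the administered substance and an AE is at least a reasonable possibility, i.e. the relationship cannot be ruled out".
- **Serious Adverse Reaction (SAR).** The row starts from an adverse event, not from an adverse reaction. It requires the event to be serious and, in the reporting investigator's opinion, "believed with reasonable probability to be due to one of the research treatments".
- **SUSAR.** "A serious adverse reaction, the nature and severity of which is not consistent with the information about the medicinal product", with the SmPC as the reference.

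Section I.2 then sets the reporting rules. For the regulator: "All SUSARs will be reported to the MHRA in addition to the MS IDREC". A fatal or life-threatening SUSAR is due "no later than 7 calendar days after the PI is first aware of the reaction"; any other is due "no later than 15 days after the PI is first aware of the reaction". Separately, every adverse event goes to MS IDREC. Those that are both related and unexpected go as soon as possible, and unrelated or expected ones within 10 working days.

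**The concern.** Two adjacent rows of the same table use different causality tests, and the stricter one applies to the more serious events. A link that cannot be excluded is enough to make an event an adverse reaction. Once the event is also serious, the investigator must hold the link to be reasonably probable before the event counts as a Serious Adverse Reaction. Because the SUSAR definition rests on that term, the stricter test carries through to the regulator's report.

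What is at stake is the MHRA report, with its fixed time limits, for serious and unexpected events of uncertain cause. The study is double-blind with 28 participants per group, so an investigator judging such an event would not know whether pitolisant or placebo had been given. In that position a possible link is easy to accept and a probable one harder to assert, so the difference between the two wordings could decide the classification.

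**Working it through.** The check is a trace of definitions; there is no figure in the plan to reproduce.

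**Step 1: the chain.** SUSAR = serious adverse reaction + not consistent with the SmPC (Section I.1). Serious Adverse Reaction = serious adverse event + reasonable probability (Section I.1). MHRA report = SUSAR only (Section I.2). I found no other text in the Protocol that brings the lower AR test back for serious events.

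**Step 2: apply it to a serious event.** The table sorts a serious event by the investigator's view of the link and by fit with the SmPC. It compares the SAR row as written with a SAR row that used the AR test.

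| Link to treatment | Consistent with SmPC? | AR? | SAR as written? | SUSAR as written? | SUSAR under the AR test? | MHRA report lost? |
|---|---|---|---|---|---|---|
| Probable | No | Yes | Yes | Yes | Yes | No |
| Probable | Yes | Yes | Yes | No | No | No |
| Possible only | No | Yes | No | No | Yes | **Yes** |
| Possible only | Yes | Yes | No | No | No | No |
| Ruled out | Either | No | No | No | No | No |

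Only one row changes: serious, not consistent with the SmPC, and possible only. A serious reaction that the SmPC already describes is not a SUSAR under either test, so it loses nothing.

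**Step 3: what still happens to that event.** It is an adverse event, so it goes to MS IDREC. If it is treated as related and unexpected, it goes as soon as possible. Suppose instead that it were placed in the slower tier. At five working days a week, 10 working days is 10 / 5 × 7 = 14 calendar days, ignoring public holidays. That is within the 15-day SUSAR limit and 14 − 7 = 7 calendar days beyond the limit for fatal or life-threatening SUSARs. What is lost in every case is the report to the MHRA; a later ethics-committee deadline arises only in the fatal or life-threatening case, and only if the slower tier is applied.

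**The case against.** The best defence is that the SUSAR row can be read generously. Its name includes the word suspected, and the term serious adverse reaction appears there in lower case. A reader could take it to mean an adverse reaction, as defined two rows earlier in the table, that happens to be serious. On that reading there is no gap. The authors may well have intended this, but the Protocol does not say so. Serious Adverse Reaction has its own row with its own wording, and a rule with fixed reporting deadlines should not depend on which reading a given investigator prefers.

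Some stronger readings are tempting, and the document does not support them.

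- **That these events go unreported.** They do not. Section I.2 sends every adverse event to MS IDREC.
- **That every serious event with a possible link loses its MHRA report.** Only those not consistent with the SmPC do, as the table shows.
- **That Section I.2 sets a third causality threshold.** It says: "Reports of related (resulted from administration of any of the research procedures) and unexpected (the type of event is not listed in the protocol". The gloss on related names what the event is attributed to and states no degree of certainty. It can be read in line with the AR row, which would put a possible-link, unexpected event in the faster ethics route. A clarifying phrase is useful, but a third threshold is not established.
- **That the two expectedness references contradict each other.** Section I.2 refers to the protocol for ethics-committee timing. The SUSAR row asks whether the event is "not consistent with the information about the medicinal product set out in its summary of product characteristics". These serve two recipients, and no error is shown to follow from the difference.

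It is also fair to say that the practical weight is small: a single dose within the stated usual range, in 56 screened healthy volunteers.

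**Conclusion.** The point holds in a limited form. As written, the SAR row is inconsistent with the AR row. The literal consequence is that a serious event outside the SmPC with a possible but not probable link does not trigger the 7-day or 15-day MHRA report. For such an event the effect is all or nothing: an MHRA report or none.

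How often this would occur cannot be sized, because the Protocol gives no rate of serious events; the number is likely to be very small. The conclusion assumes that the investigator distinguishes a possible from a probable link and applies the SAR row as worded. Sample size, power and the type I error rate are not affected. This is a wording correction worth making because it concerns safety reporting and costs little.

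**What to change.** Reconcile the SAR row of Section I.1 with the AR row, so that a Serious Adverse Reaction is an adverse reaction, under the same causality test, that also meets the seriousness criteria. The SUSAR row then takes on that test without further change. In Section I.2, add that related is judged by the same test.

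The cost is a protocol wording amendment and possibly a few more expedited reports. One consequential check is needed: the code-break paragraph in Section I.3 also uses the term serious adverse reactions, and data from unblinded participants are kept out of the analysis. That paragraph has its own condition, that knowing the allocation must be clinically important, so the sponsor should confirm that it still reads as intended once the definition is aligned.
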